14.1 Drug Exposure

The analysis of drug exposure will include summaries of the total dose received by treatment arm and visit (mean, Standard Deviation (SD), median, min and max). An exploratory analysis of how drug exposure may be related to changes in safety assessments will also be performed.

14.2 Adverse Events

Some maternal events related to prenatal period, labour, delivery and the postnatal period are commonly experienced and are therefore exempt from safety reporting unless fatal, life threatening, medically important or results in persistent disability or incapacity (see Appendix for the list of exempted AEs). However, exempted AEs were recorded prior to protocol version 6.0 (dated 02 May 2019) and before the implementation of exemptions in safety reporting. The exempted AEs will be excluded in the analyses below.

The analysis of adverse events will include:

- A summary (by treatment arm) of the number of Adverse Events (AEs) reported (counts), and the number of participants experiencing any adverse event (counts and percentages) will be presented. Treatment arms will be compared using the chi-squared test.
- Summaries of each adverse event (coded as Preferred Term and System Organ Class) by treatment arm will be provided. Summaries will include number of events, number of participants (counts and percentages), severity and highest grade. Comparisons between treatment arms using chi-squared or Fisher's exact test (where enough information is available) will be presented. Note that the highest grade will be considered if a participant has different grades for the same adverse event.

EMERGE NUIG-2016-01, Statistical Analysis Plan Version 1, 21/03/2023

- Summaries of patients with AEs definitely, probably or possibly related to metformin, Insulin or interaction between metformin and Insulin, by preferred term and treatment arm will be given.

Separate table summaries will be presented for AEs occurring on the mother and for AEs occurring in the baby.

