859 5. DTSQ (gestational week 38 (+/- 1 week) or as soon as possible thereafter)
860 6. Study Drug Accountability (every 4 weeks)

861
862 **8.3.3. Delivery Visit**

863
864 The delivery visit will occur up to 72 hours post-delivery, while the participant is in the post natal ward.
865 Should the participant be discharged early, or it is not possible to see the participant within the visit
866 window (e.g. delivery occurs out of hours), every effort will be made to gather the information from the
867 medical notes or through telephone contact. The following data will be collected and procedures will
868 be performed:

869
870 1) Vital signs (heart rate, BP)
871 2) Review of concomitant medications
872 3) Review of adverse events (mother and baby)
873 4) Last routine HbA1c recorded
874 5) Delivery information (time, date and mode of delivery, and complications)

875 6) Feeding method initiated
876 7) Neonatal procedures (status of baby, sex, neonatal measurements, Apgar score,
877 hypoglycaemia, respiratory distress, jaundice and congenital anomalies)
878 8) Neonatal care unit data
879 9) Neonatal medical resources
880

881 **8.3.4. Phone Visit (Visit 1 Post-Partum)**

882
883 A phone visit will take place 4 weeks (+/- 7 days) post-partum. The following data will be collected:
884

885 1) Status of the baby
886 2) Current Feeding method
887 3) Neonatal complications
888 4) Discharge date
889 5) Questionnaires (EQ5D-5L, Rowan Questionnaire)
890 6) Adverse Events (mother and baby)

891 An appointment will be scheduled for the 12 week post-partum visit by the research nurse.
893

894 **8.3.5. 12 Week Post-Partum Visit (Visit 2 Post-Partum)**

895
896 The post-partum visit will take place 12 weeks post-partum (+/- 4 weeks) and will be conducted in
897 person. The following data will be collected and procedures will be performed:
898

899 1) Physical measurements (heart rate, BP, height, weight and waist circumference)
900 2) 75g OGTT
901 3) Laboratory tests (see section 8.4.5)
902 4) Questionnaires (EQ5D-5L)
903 5) Study medication returns
904 6) Status of baby
905 7) Neonatal complications
906 8) Current feeding method
907 9) Return Glucometer and data download
908 10) Medical care received since delivery
909 11) Adverse Events (mother and baby)

910
911 An outline of scheduled study assessments and procedures are outlined below in figure 2.
912

913
914
915
916
917
918
919

Schedule of Visits											

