1210 site will instruct the participant to go back to the previous dose and then try again to increase the dose
1211 after 4-7 days. If the participant cannot tolerate the study medication at the higher dose, but can
1212 tolerate the study medication at a lower dose, the participant may continue at that lower dose for the
1213 treatment period.

1214 **9.1.3. Placebo Group**

1215 Participants randomised to the placebo arm will receive placebo in addition to usual care. Placebo will
1216 be titrated according to the dosing schedule to achieve the pre-specified glucose targets (fasting
1217 ≤5mmol/l, 1hour post prandial ≤ 7mmol/l). Placebo tablets will commence at 1 tablet per day and will
1218 be increased to a maximum of 5 tablets per day over 10 days as with the treatment group.

1219 **9.1.4. Requirement for Insulin**

1220 Insulin will be commenced in each group as per normal practice if 2 or more home glucose readings
1221 are outside the pre-specified glucose targets (fasting ≤ 5mmol/l, 1hour post prandial ≤ 7mmol/l)
1222 (without reason) despite maximum oral therapy and MNT at any clinic visit. For this reason, insulin is
1223 considered a non-IMP in this trial (see safety reporting for NIMP section 10.3.3.). If insulin is initiated,
1224 tablets will also be continued at the maximum tolerated dose. Off study metformin is unlikely to be
1225 used as this is not routine clinical practice currently. The intervention will continue up to birth of the
1226 infant or end of pregnancy due to pregnancy loss.

1227

1228 **9.2. Formulation, packaging, and handling**

1229 The IMPs are Glucophage (Metformin) 500mg film-coated tablets and placebo to match tablets
1230 supplied to the trial by the marketing authorisation holder Merck Santé (France).

1231

1232 The tablets will be repacked for the trial into bottles containing 170 active or placebo tablets and each
1233 bottle will be labelled according to Annex 13 requirements.
1234 The Sponsor has contracted MODEPHARMA for arranging the clinical trials packaging, labelling, QP
1235 release and distribution of trial IMPs in compliance with Good Manufacturing Practice (GMP) and
1236 Good Distribution Practice (GDP). Please refer to the Summary of product Characteristics and
1237 Investigational Medicinal Product Dossier (IMPD) for further details about the IMP manufacture and
1238 labelling.

1239

1240 **9.3. Storage of study treatments(s)**

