10.2.3. Assessment of severity

1596

1597

The investigator will make an assessment of severity for each AE/SAE and record this on the CRF according to one of the following categories:

1598

1599

- Mild: An event that is easily tolerated by the participant, causing minimal discomfort and not interfering with every day activities.
- Moderate: An event that is sufficiently discomforting to interfere with normal everyday activities.
- Severe or medically significant: An event that prevents normal everyday activities.
- Life threatening: An event that has life-threatening consequences

1600

1601

1602

1603

1604

1605

1606

1607

Note: the term 'severe', should not be confused with 'serious' which is a regulatory definition based on

1608

participant/event outcome or action criteria

1609 **10.2.4. Assessment of expectedness**

1610

1611 An expectedness assessment will be carried out by the sponsor for each serious adverse reaction to
1612 the IMP or an interaction between the IMP and non-IMP. The expectedness of a serious adverse
1613 reaction will be determined by the sponsor according to the reference safety information as contained
1614 in section 4.8. of the SmPC for Metformin.

1615

1616 **10.3. Reporting Responsibilities of the investigator**

1617

1618 **10.3.1. Adverse Events/Serious Adverse Events**

1619

1620 Any AE whose onset occurred after the time of informed consent and the last completed visit,
1621 observed by the investigator or reported by the participant, whether or not attributed to the study
1622 medication, will be recorded on the AE form in the CRF. The Site Investigator or delegate will follow
1623 AE's and SAE's reported during the treatment period until resolved, considered stable, or completion
1624 of participant participation in the EMERGE trial (i.e. 12 week Postpartum Visit). Follow up information
1625 will be sought and submitted as it becomes available. All SAEs will be followed up until resolution or
1626 they are clearly determined to be due to a participant's stable or chronic condition or intercurrent
1627 illness(es).

1628

1629 The following information will be recorded in the adverse event form: Adverse event term, description,
1630 date of onset, outcome, date of resolution, seriousness, severity, assessment of relatedness to the
1631 study medication, assessment of relatedness to non-IMP, and assessment of relatedness to

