6.1 General Study design and Plan

The EMERGE study is a phase III, parallel, randomised double-blind, placebo-controlled, trial of metformin (in addition to usual care) versus usual care in 550 women with Gestational Diabetes Mellitus (GDM) across 2 sites in Ireland, followed until 12 weeks post-partum (+/- 4 weeks).

It will comprise 3 steps; 1) screening, 2) treatment, and 3) follow up. Eligible women will be randomised to one of two groups; treatment group or placebo group.

Women randomised to the metformin group will receive metformin 500mg Once Daily (OD), with the dose titrated upwards every 2 days over 10 days increasing to a maximum of 2500mg metformin daily (5 tablets) or maximum tolerated dose, in addition to usual care (exercise and MNT), and taken until delivery.

Participants randomised to the placebo group will receive 1 placebo tablet OD, with the dose titrated upwards every 2 days over 10 days increasing to a maximum

[figure not shown]
EMERGE NUIG-2016-01, Statistical Analysis Plan Version 1, 21/03/2023

of five placebo tablets daily, in addition to usual care (exercise and MNT), and taken until delivery.

Participants will be followed up at 4 (+/- 7days) and 12 weeks (+/- 4 weeks) post-partum for additional maternal and neonatal outcomes.

The control and metformin groups will receive usual care, which consists of medical nutritional therapy (MNT) and information on exercise provided by the Diabetes team. The Diabetes team or trained delegate will instruct women on using a glucometer, and the women will perform 7-point glucose testing before and 1 hour after meals and before bed. Women will be supported by telephone contact from the Diabetes team or trained delegate weekly throughout gestation and attend at 2-4 weekly intervals at an antenatal/diabetes clinic. Usual care is outlined in more detail in section 9.1.1 of the protocol.

EMERGE NUIG-2016-01, Statistical Analysis Plan Version 1, 21/03/2023

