14.3 Deaths, withdrawal, Serious Adverse Events and other Significant Adverse Events

Serious adverse events (SAEs) will be analysed in the same fashion as AEs. Withdrawals will be summarised as the number and percentage of patients who were withdrawn from the study by treatment arm.

14.3.1 *Withdrawal due to Adverse Events*

Withdrawals due to adverse events will be summarised as the number and percentage of patients who were withdrawn by treatment arm.

14.3.2 *Deaths*

In the unlikely case that deaths occur they will be summarised as the number and percentage of participants (mother or baby) who died within the study period by treatment arm.

14.3.3 *Other AE Assessments*

No other assessments or analyses are planned.

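### The SAP compares maternal AEs and SAEs only over the whole recording period, to 12 weeks after birth, although study drug stops at delivery; an on-treatment comparison should be added beside it

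*SAP*

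**What the plan says.** **Drug period.** SAP 6.1 describes tablets in both arms as added to "usual care (exercise and MNT), and taken until delivery". Protocol 9.1.4 agrees: "The intervention will continue up to birth of the" infant, or to the end of the pregnancy if it is lost.

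**AE recording period.** Protocol 10.3.1 records "Any AE whose onset occurred after the time of informed consent and the last completed visit", which can only sensibly mean onset between those two points. Protocol 8.3.4 and 8.3.5 collect AEs in the mother at 4 and at 12 weeks post-partum, the latter with a window of 4 weeks either way. Randomisation may follow screening by up to 7 days (Protocol 8.3.1).

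**Analysis.** SAP 14.2 gives "A summary (by treatment arm) of the number of Adverse Events (AEs) reported (counts), and the number of participants experiencing any adverse event" and compares arms by chi-squared test. It adds tables by Preferred Term and System Organ Class with chi-squared or Fisher comparisons, and a table of AEs judged related to metformin, insulin or their interaction. Mother and baby are tabulated separately. Events exempt from safety reporting are left out. SAP 14.3 analyses SAEs as AEs, and 14.3.3 closes with "No other assessments or analyses are planned". The safety set (SAP 9.3) requires one dose: it limits which women count, not which of their events count.

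**The concern.** The safety question is whether metformin, added during pregnancy, harms the mother. The planned comparisons mix weeks in which the arms differ in exposure with weeks in which neither arm takes tablets. The trial is described as having screening, treatment and follow-up periods (Protocol synopsis; SAP 6.1), but the AE analysis does not use that division.

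Where an outcome has background occurrence after birth, the extra events are similar in both arms and move the ratio toward 1. The direction is not neutral: it makes a difference in harm harder to see. That matters in a trial whose stated use is to support metformin from diagnosis in a broad GDM population.

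**Working it through.** The documents give no off-drug share and no power for AEs, so there is no planned figure to reproduce.

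**Inputs**
- Entry at 24 to 28+6 weeks (SAP 6.2). The protocol sets only the upper limit of 28+6 (8.2.2, 8.3.1).
- End of pregnancy at or before 40 weeks (SAP 3); 39 weeks is an assumption.
- Post-partum visit at 12 weeks, window 8 to 16.
- 535 participants (SAP 8.1), 1:1, so about 267 per arm; two-sided 0.05.

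**Step 1: off-drug share of maternal AE time.** f = post-partum weeks / (weeks on drug + post-partum weeks). Pre-dose time, a week or so at most, is ignored.

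| Entry (weeks) | Birth (weeks) | Weeks on drug | Post-partum weeks | f |
|---|---|---|---|---|
| 24 | 40 | 16 | 12 | 12/28 = 43% |
| 28 | 40 | 12 | 12 | 12/24 = 50% |
| 28+6 | 40 | 11.1 | 12 | 12/23.1 = 52% |
| 28+6 | 39 | 10.1 | 12 | 12/22.1 = 54% |
| 24 | 40 | 16 | 8 | 8/24 = 33% |
| 28+6 | 39 | 10.1 | 16 | 16/26.1 = 61% |
| 20 | 40 | 20 | 12 | 12/32 = 38% |
| 12 | 40 | 28 | 12 | 12/40 = 30% |

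**Step 2: effect on a rate ratio.** Assume the same weekly background rate before and after birth, and no drug effect after birth. Then pooled ratio = (1 − f) × RR + f.
- f = 0.50: RR 1.5 gives 0.75 + 0.50 = 1.25; RR 2.0 gives 1.00 + 0.50 = 1.50.
- f = 0.43 to 0.54: RR 1.5 gives 1.29 to 1.23; RR 2.0 gives 1.57 to 1.46.
- f = 0.30: RR 1.5 gives 1.35; RR 2.0 gives 1.70.

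**Step 3: effect on what the SAP actually compares, the proportion of women with an event.** Risk = 1 − exp(−rate × time). Take 12 weeks on drug and 12 weeks off. The control risk over the on-drug weeks and the hazard ratio (HR) are illustrative; neither is in the documents.

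| On-drug control risk | HR | On-treatment risks | Ratio; difference; power | Whole-period risks | Ratio; difference; power |
|---|---|---|---|---|---|
| 10% | 1.5 | 10.0% v 14.6% | 1.46; 4.6 points; 37% | 19.0% v 23.2% | 1.22; 4.2 points; 22% |
| 10% | 2.0 | 10.0% v 19.0% | 1.90; 9.0 points; 84% | 19.0% v 27.1% | 1.43; 8.1 points; 60% |
| 40% | 1.5 | 40.0% v 53.5% | 1.34; 13.5 points; 88% | 64.0% v 72.1% | 1.13; 8.1 points; 52% |

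The risk difference falls proportionately less than the excess ratio, and only slightly when the event is uncommon. With no post-partum background for the event, the two analyses coincide: at 10% and HR 2.0 both give a ratio of 1.90 and power of 84%.

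**The case against.** A reader might infer that any metformin harm is diluted. The documents do not support that. Dilution needs off-drug background for the same event; one confined to pregnancy keeps its full contrast in its Preferred Term table. Nor is the any-AE total the only analysis: SAP 14.2 has Preferred Term, System Organ Class and related-AE tables, and SAP 14.1 plans an exploratory look at exposure and safety, so 14.3.3 should not be read as excluding everything else. These safeguards are partial. The related-AE table rests on causality judgement and has no stated between-arm test, and the exposure analysis defines no on-treatment AE window.

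Share of time is also not share of events. AEs are reviewed about every 2 weeks before birth but only at delivery, 4 weeks and 12 weeks afterwards. Protocol 10.2 exempts mastitis, obstetric wound infection and post-partum haemorrhage unless a graver criterion applies. That lowers post-partum background. But common gastrointestinal effects of metformin are exempt too, unless they lead to hospitalisation or stopping study drug, which removes on-drug signal. The net balance is unknown, so equal weekly rates are an illustration, not an estimate.

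A further tempting step is to make an on-drug window the main comparison, ending at last dose plus a lag. That would tie observation time to tolerability after randomisation and could miss harm that arises in pregnancy but shows after birth. The whole-period comparison keeps every recorded event in its randomised arm and should stay. This objection stands, and it shapes the fix. Pre-dose events add little: the gap is short, and the visit schedule (Protocol Figure 2) has no AE entry at Visit 1.

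**Conclusion.** The point holds in a limited form. Tablets stop at delivery, maternal AEs run on for a further 8 to 16 weeks, and no on-treatment comparison is planned. The SAP does not itself state the AE period; it follows from the protocol's recording window and the absence of any restriction in SAP 9.3, 14.2 or 14.3.

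The off-drug share is 43% to 54% for entry at 24 to 28+6 weeks, birth at 39 to 40 weeks and a 12-week visit. A flat statement that half of AE time is off drug would go too far, since earlier entry under the protocol brings it to about 30% to 38%. Actual gestation at entry and birth, and actual AE rates, are not in the documents.

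The consequence is attenuated ratios and lost power for any-AE, any-SAE and system-organ-class totals, of the size shown above if weekly background rates are equal. It does not show that the planned safety analysis is invalid or that a specific harm would be hidden.

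**What to change.** In SAP 14.2 and 14.3, beside the planned whole-period tables, add the same between-arm comparison of maternal AEs and SAEs for events with onset from first dose (or first dispensing date) to delivery, regardless of whether tablets were stopped early. Show post-partum events in a separate column. Keep the whole-period comparison, and leave the baby AE tables as they are.

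This is a cheap improvement: SAP wording and one derived period flag. AE onset date (Protocol 10.3.1), delivery date (Protocol 8.3.3) and dispensing date (SAP 12.4) are already recorded; a first-dose date is not explicitly listed, hence the dispensing date as fallback.

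The costs are a few more tables, fewer events per column, and a window whose length varies with gestation at delivery. Gestation at delivery is itself a secondary endpoint (SAP 5.2.2), so the window could differ between arms, which is one more reason to read the two comparisons together.

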14.3 Deaths, withdrawal, Serious Adverse Events and other Significant Adverse Events

Serious adverse events (SAEs) will be analysed in the same fashion as AEs. Withdrawals will be summarised as the number and percentage of patients who were withdrawn from the study by treatment arm.

14.3.1 *Withdrawal due to Adverse Events*

Withdrawals due to adverse events will be summarised as the number and percentage of patients who were withdrawn by treatment arm.

14.3.2 *Deaths*

In the unlikely case that deaths occur they will be summarised as the number and percentage of participants (mother or baby) who died within the study period by treatment arm.

14.3.3 *Other AE Assessments*

No other assessments or analyses are planned.

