1101 consider it necessary to un-blind for clinical care of the participant, the treating clinician will be un-
1102 blinded. All other staff must remain blinded to treatment, including the participant. All participants
1103 should resume study treatments after recovery if it is medically appropriate to do so and should be
1104 followed until the end of the study.

1105

1106 Emergency unblinding will be available on the web-based randomisation service.

1107

1108 **8.7. Definition of end-of-trial**

1109

1110 The end of trial will be the date of the last visit of the last participant post-partum. The Sponsors
1111 and/or Data safety and monitoring board/trial steering committee have the right at any time to
1112 terminate the study for clinical or administrative reasons.

1113

1114 The end of the study will be reported to the approving EC and HPRA within 90 days of the end of the
1115 clinical trial, or within 15 days if the study is terminated prematurely by the Sponsor or the Sponsors

1116 Representative. The EU Declaration of the End of Trial form must be used for this. The investigators
1117 will inform participants and ensure that the appropriate follow-up is arranged for all involved.
1118

1119 **8.7.1. Premature termination of the study**

1120
1121 The trial may be terminated prematurely if:

1123 • new information about safety or efficacy appears
1124 • there is unsatisfactory progress of the study
1125 • if deemed necessary by the DSMB

1126
1127 If the trial ends prematurely then the HPRA and the approving EC will need to be informed as
1128 required.

1129
1130 **8.8. Discontinuation/withdrawal of participants from study treatment**

1131
1132 Participants have the right to voluntarily discontinue study treatment or withdraw from the study at any
1133 time for any reason without any consequences. The investigator has the right to discontinue a
1134 participant from study treatment or withdraw a participant from the study at any time if it is in the best
1135 interest of the participant, in circumstances such as:

1136
1137 1. any medical condition that the investigator or sponsor determines may jeopardise the
1138 participant's safety if she continues receiving the study treatment
1139 2. ineligibility (either arising during the study or retrospectively having been overlooked at
1140 screening)
1141 3. an adverse event which requires discontinuation of the study medication
1142 4. renal or hepatic concerns, shock or sepsis

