1143 5. lack of compliance with the study and/or study procedures (e.g., dosing instructions, study
1144 visits).

1145
1146 All participants who discontinue study medication will be invited to continue with protocol specified
1147 follow-up procedures. The only exception to this requirement is when a participant withdraws consent
1148 for all study procedures and contact.

1149
1150 If a participant discontinues study medication, or withdraws full study consent before completing the
1151 study, the reason for this must be entered on the appropriate case report form (CRF) page.
1152

1153 If a participant is withdrawn due to an adverse event, the investigator will arrange for follow-up visits
1154 until the adverse event has resolved or stabilised.
1155

1156

1157 **9. TREATMENT OF TRIAL PARTICIPANTS**

1158

1159 **9.1. Description of study treatments**

1160

1161 Once a diagnosis of GDM is made, participants will be randomised to either the placebo or metformin
1162 arm and medication will commence and continue in addition to usual care.

1163

1164 **9.1.1. Usual Care**

1165

1166 All participants participating in the Emerge trial will receive usual care as follows: Following a
1167 diagnosis of GDM participants will be seen by the diabetes team or trained delegated personnel within
1168 1 week of diagnosis who will explain the diagnosis of GDM and its implications for her and her infant.
1169 The DNS or trained delegated personnel will instruct participants on the use of a glucometer and the
1170 participants will perform 7-point glucose testing before and 1 hour after meals and before bed.
1171 Glucose targets of </=5 mmol/l fasting and before meals and </= 7mmol/l 1 hour after meals will be
1172 given. Literature will be given and a contact name and telephone number given for any queries or
1173 urgent matters. Participants will be seen either by the diabetes physician/DNS/or trained delegate to
1174 impart dietary advice (medical nutritional therapy (MNT)) and information on exercise. Participants will
1175 be supported by telephone contact from the DNS or trained delegate weekly throughout gestation and
1176 attend at 2-4 weekly intervals at an antenatal/diabetes clinic.

1177

1178 Two weeks following the commencement of MNT and exercise, each participant is reviewed at the
1179 diabetes/antenatal clinic to review blood sugars and decide on the need for insulin intervention. At this

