1632 interaction between IMP and non-IMP, and action taken with study drug. The Site Investigator is
1633 responsible for the assessment of severity (intensity), causality/relatedness to IMP, non-IMP or an
1634 interaction between IMP and non-IMP, for all AEs and SAEs. An SAE should also be substantiated by
1635 a source document(s). Follow-up information should be provided as necessary.

1636

1637 It will be left to the investigator's clinical judgment whether or not an AE is of sufficient severity to
1638 require the participant's removal from medication. A participant may also voluntarily withdraw from
1639 medication due to what he or she perceives as an intolerable AE. If either of these occurs, the
1640 participant must undergo an end-of-study assessment and be given appropriate care under medical
1641 supervision until symptoms cease or the condition becomes stable.

1642

1643 **10.3.2. Timelines for reporting**

1644

1645 Adverse event information will be reported by site personnel in a timely fashion from the time the site
1646 becomes aware of the event.

1647

1648 Serious adverse event information will be reported by site personnel within 24 hours to the sponsor
1649 from the time the site becomes aware of the event, except for those that the protocol identifies as not
1650 requiring immediate reporting. The site team are considered aware of an adverse event from the time
1651 of first notification of the first member of the EMERGE site team, as per the Site Delegation Log. All
1652 SAE's will be submitted by the site by completing the required fields on the AE CRF within 24 hours of
1653 site awareness of the event. A valid SAE report must include all of the following:

1654

- 1655 • Adverse event term (based on what is known at the time of reporting)
- 1656 • Seriousness criteria
- 1657 • Severity

1658 • Causality assessments (for metformin/placebo, insulin [if applicable] and the potential
1659 interaction between metformin/placebo and insulin [if applicable])
1660 • Investigator sign-off

1661
1662 The immediate report will be followed by detailed, written reports. The immediate and follow-up
1663 reports will identify participants by unique code numbers.
1664

1665 **10.3.3. Safety Reporting for Non-IMP**

1666
1667 Insulin is considered a non-IMP and therefore must follow safety reporting guidelines for non-IMP.
1668 All AEs and SAEs considered by the investigator to be related to the non-IMP will be reported to the

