11.1 Subject Disposition

Different variables from the CRF will be considered to determine the number of patients who reached the various stages of the study. The following counts will be reported by study group:

- Number of participants randomised
- Number of randomised participants who received study medication at least once
- Number of participants who completed the study medication.
- Number of participants who had the delivery.
- Number of participants who completed the post-delivery follow-up visit.
- Number of participants who withdrew the study before completion.

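### SAP 14.3.1 counts adverse-event withdrawals at study level, or leaves the level unclear, so no planned table gives adverse-event discontinuation of study drug by arm

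*SAP*

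**What the plan says.** SAP 14.3 defines the general summary: "Withdrawals will be summarised as the number and percentage of patients who were withdrawn from the study by treatment arm". Subsection 14.3.1 follows directly: "Withdrawals due to adverse events will be summarised as the number and percentage of patients who were withdrawn by treatment arm". It does not repeat the reference to the study. SAP 14.3.3 then closes the section: "No other assessments or analyses are planned".

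Protocol 8.8 works with two events. It lets the investigator discontinue a "participant from study treatment or withdraw a participant from the study at any time if it is in the best" interest of the participant, and one of the listed circumstances is "an adverse event which requires discontinuation of the study medication". On what follows, it says: "All participants who discontinue study medication will be invited to continue with protocol specified" follow-up procedures. The one exception is a woman who withdraws consent to all procedures and contact. The reason for either event must be entered on the CRF.

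Protocol 10.3.1 lists the contents of the AE form, ending with relatedness to an "interaction between IMP and non-IMP, and action taken with study drug". The same section requires an end-of-study assessment when a woman comes off medication because of an AE.

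The nearest other SAP output is a disposition count in 11.1: "Number of participants who completed the study medication".

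**The concern.** The trial asks whether metformin should be given to every woman at GDM diagnosis rather than only to those in whom diet and exercise fail. How many women cannot continue the tablets because of side effects is a central part of the answer. The protocol itself treats this as a signal: in section 10.2 the exemption from reporting for metformin gastrointestinal effects lapses if study drug is stopped.

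The one SAP table whose title suggests this quantity appears to count something else. The protocol's document history says version 6 amended 8.8 to clarify the difference between stopping medication and withdrawing consent. The SAP names version 6 as a source but does not carry the distinction into 14.3.1. The better the sites keep women in follow-up after they stop tablets, the fewer AE-related stops a study-level table will show. A reader of the report could then take a low withdrawal figure as evidence of good tolerability.

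**Working it through.** The plan states no figure on this point, so there is nothing to reproduce. The check sets the sections side by side.

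**1. Who is counted.** Take a woman who stops study drug for an AE during pregnancy.
- She also leaves the study: counted under either reading of 14.3.1.
- She accepts follow-up under Protocol 8.8: not counted if 14.3.1 takes its unit from 14.3; counted only if 14.3.1 is read as withdrawal from medication.

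**2. Whether another output supplies the number.**

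| SAP section | What it gives | What is missing |
|---|---|---|
| 11.1 | Number completing study medication, by group | Reason for not completing |
| 12.4 | Adherence against the maximum tolerated dose, per visit and overall | Cause; permanent stop versus missed tablets |
| 14.1 | Total dose by arm and visit | Cause of a low dose |
| 14.2 | AEs by term, severity and relatedness, by arm | Whether the event led to stopping study drug |

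None crosses drug stopping with an AE reason by arm.

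**3. Direction.** During the treatment period, a woman withdrawn from the study for an AE has also stopped study drug. So the study-level count in that period can equal the number of AE-related drug stops or fall below it, but cannot exceed it.

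**4. How the shortfall behaves (illustration; all rates assumed).** Let N be women per arm, p the proportion stopping drug for an AE, and f the share of those who also leave the study. The count shown is N × p × f. SAP 8.1 sets a total of 535, so 535 / 2 = 267.5, about 267 per arm. Counts are rounded to whole women, metformin first.

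| Assumed p | f = 1 (all stops) | f = 0.5 | f = 0.25 |
|---|---|---|---|
| 5% v 2% | 13 v 5 (3.0 points) | 7 v 3 (1.5) | 3 v 1 (0.7) |
| 12% v 4% | 32 v 11 (7.9 points) | 16 v 5 (4.1) | 8 v 3 (1.9) |

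Example: 267 × 0.12 = 32.0 and 267 × 0.04 = 10.7, so 32 v 11 and (32 − 11) / 267 = 7.9 points. With f = 0.5, 16.0 and 5.3 give 16 v 5 and (16 − 5) / 267 = 4.1 points. Apart from rounding, the difference shown is f times the true one when f is the same in both arms. The documents give neither p nor f.

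**The case against.** Four arguments weigh against the point.

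*14.3.1 says only that patients were withdrawn.* This is correct. Protocol 10.3.1 speaks of withdrawing from medication because of an AE, and the heading of 8.8 joins discontinuation and withdrawal under study treatment. A programmer could therefore build 14.3.1 as drug withdrawal. That makes the section ambiguous rather than plainly wrong. But 14.3.1 sits under a sentence that names the study as the unit, and two programmers could produce different tables, so it needs a definition on either reading.

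*Women who stop may not stay.* Protocol 8.8 invites them to continue and does not guarantee that they do. It also allows withdrawal from the study, and 10.3.1 calls for an end-of-study assessment. Some AE-related stops will therefore appear in a study-level table. Remaining in follow-up is the default, not a certainty.

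*SAP 14.2 would show the signal.* In part it would. Diarrhoea that stops the drug is not exempt under Protocol 10.2, so it should appear in the by-arm AE tables with a test. But nausea, vomiting and flatulence are also listed as common pregnancy symptoms, where the exemption has no clause about stopping drug. Events of any kind carry no drug-stop flag in 14.2.

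*The other outputs would reveal an arm imbalance.* Completion, adherence and dose would show a gap in drug taking, but not that AEs caused it.

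There is also a stronger reading to resist. A reader might take the 8% non-adherence in the sample-size section, compute 267 × 0.08 = 21 women on metformin, and infer that all would vanish from the table and leave 0% in each arm. The documents do not support this. The 8% is a planning figure for non-adherence without regard to cause, and nothing makes it an AE-related stopping rate or an upper bound. No placebo rate is given. A zero count needs every woman who stops to stay in the study.

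**Conclusion.** The point holds as a gap in the planned safety reporting. Read with 14.3, SAP 14.3.1 counts AE withdrawals at study level; read alone, it is ambiguous. No other planned output gives discontinuation of study drug due to an AE by arm.

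On the study-level reading, AE-related stops in the treatment period would be understated, by an unknown amount. That the difference between arms would also shrink needs two further assumptions: that such stops are commoner on metformin, and that a similar share of those who stop leave the study in each arm. The primary analysis, the analysis sets and data collection are not affected. The change is still worth making, because tolerability bears directly on the trial's question and the data already exist.

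**What to change.** - Define SAP 14.3.1 as permanent discontinuation of study medication due to an AE, with number and percentage by arm in the safety set. Derive it from the CRF reason for discontinuation (Protocol 8.8) and the action-taken field of the AE form (Protocol 10.3.1).
- Report withdrawal from the study due to AEs on a separate line.
- Reconcile Protocol 8.8, which continues follow-up after stopping, with 10.3.1, which asks for an end-of-study assessment, so that sites record the two categories consistently.

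The cost is a change of SAP wording, one table, and a check that the two source fields agree. No new data are needed.
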